AE: adverse event, ACTH: adrenocorticotrophic hormone, ADA: anti-drug antibodies; BCG: *Bacillus Calmette Guérin*, BP: blood pressure; CIS: carcinoma in situ; CT: computed tomography, ECG: electrocardiogram, ECOG PS: Eastern Cooperative Oncology Group Performance Status, EORTC-QLQ-C30: European Organisation for Research and Treatment of Cancer Quality of Life Questionnaire-30 (items); EOT: end of treatment; MRI: magnetic resonance imaging, NAb: neutralizing antibodies; NMIBC: non-muscle invasive bladder cancer, PGIC: Patient Global Impression of Change; PGIS: Patient Global Impression of Severity; PK: pharmacokinetics, PTAB: Patient Treatment Administration Burden; Q4W: every 4 weeks; TSQ: Treatment Satisfaction Questionnaire

End of Treatment Visit and Follow-Up Period – Cohort A

	EOT*	Post-Treatment Period			*EOT: End of Treatment visit will take place within 7 days of the last dose of PF-06801591 or BCG (whichever is later) or decision to discontinue both drugs. This includes participants that complete the full 25 cycles of treatment as well as participants that discontinue treatment early. **Safety Follow-Up: All participants enter safety follow-up period at EOT. Visits at 30, 60, and 90 days post-EOT. ***Disease Follow-Up: Participants with no recurrence of high-grade disease, disease progression, or persistence of CIS before EOT will be assessed Q12W for 2 years after randomization and Q24W thereafter until recurrence of high-grade disease or disease progression, consent withdrawal, lost to follow-up, or death. Timing of disease assessment is fixed according to the calendar, starting with randomization and should not be adjusted. ****Survival Follow-Up: Q12W until consent withdrawal, lost to follow-up, death, or end of study (5 yrs from last participant randomized). Sponsor may request that sites complete additional survival follow-up to facilitate planned analyses as needed.
		Safety Follow-Up **	Disease Follow-Up ***	Survival Follow-Up ****	
Visit Window (Days)	+7	±7	±7	±7	
Physical Examination	X	X			Physical examinations should be performed according to clinical practice. Any abnormalities should be recorded as adverse events. See Section 8.2.1.
Weight	X	X			
Vital Signs	X	X			BP and pulse rate will be performed. Any abnormalities should be recorded as AEs. See Section 8.2.2.
Contraception check	X	X			
ECOG PS	X				

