For participants in Cohorts A, B1, and B2, a cycle is defined as the time from Day 1 dose to the next Day 1 dose. Participants will receive a single dose of PF-06801591 on Day 1 of each cycle. In Cohort A, a cycle will be 28 days (± 3 days prior to Cycle 4, ± 7 days for Cycle 4 through EOT), in Cohort B1, a cycle will be 28 days (± 3 days prior to Cycle 2, ± 7 days for Cycle 2 through EOT), and in Cohort B2, a cycle will be 42 days (± 3 days prior to Cycle 2, ± 7 days for Cycle 2 through EOT) for SC administration. Each participant may receive PF-06801591 until the earliest of the following events: completion of study treatment (Cycle 25 for Cohorts A and B1 and Cycle 17 for Cohort B2) recurrence of high-grade disease or progression of disease, unacceptable toxicity, withdrawal of consent, participant no longer willing to participate in trial, or study termination.

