Grade 2 AST or ALT > 3.0 to \leq 5 x ULN and/or total bilirubin > 1.5 to \leq 3 x ULN	-Withhold study treatment -Increase frequency of monitoring to every 3 days	-If returns to Grade \leq 1: -Resume routine monitoring; resume study treatment. -If elevation persists > 5 to 7 days or worsens: -Treat as Grade 3 to 4.
Grade 3 to 4 AST or ALT > 5 x ULN and/or total bilirubin > 3 x ULN	-Permanently discontinue study treatment -Increase frequency of monitoring to every 1 to 2 days -1.0 to 2.0 mg/kg/day prednisone or equivalent -Add prophylactic antibiotics for opportunistic infections -Consult gastroenterologist/hepatologist -Consider obtaining MRI/CT scan of liver and liver biopsy if clinically warranted	-If returns to Grade \leq 1: -Taper steroids over at least 1 month. -If does not improve in > 3 to 5 days, worsens or rebounds: -Add mycophenolate mofetil 1 gram (g) twice daily. -If no response within an additional 3 to 5 days, consider other immunosuppressants per local guidelines.

Renal irAEs		
Grade of Creatinine Increased (NCI-CTCAE v5.0)	Initial Management	Follow-up Management
Grade 1 Creatinine increased > ULN to 1.5 x ULN	-Continue study treatment	-Continue renal function monitoring. -If worsens: Treat as Grade 2 to 3 or 4.
Grade 2 to 3 Creatinine increased > 1.5 and \leq 6 x ULN	-Withhold study treatment -Increase frequency of monitoring to every 3 days -1.0 to 2.0 mg/kg/day prednisone or equivalent. -Add prophylactic antibiotics for opportunistic infections -Consider renal biopsy	-If returns to Grade \leq 1: -Taper steroids over at least 1 month, and resume study treatment following steroids taper. -If worsens: -Treat as Grade 4.
Grade 4 Creatinine increased > 6 x ULN	-Permanently discontinue study treatment -Monitor creatinine daily -1.0 to 2.0 mg/kg/day prednisone or equivalent. -Add prophylactic antibiotics for opportunistic infections Consider renal biopsy -Nephrology consult	-If returns to Grade \leq 1: Taper steroids over at least 1 month.

Cardiac irAEs		
Myocarditis	Initial Management	Follow-up Management

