### **5.2.7. Definition of on-treatment period**

Safety endpoints will be summarized based on the on-treatment period unless otherwise specified.

On-treatment period is defined as the time from the first dose of study treatment through minimum (30 days + last dose of study treatment, start day of new anti-cancer drug therapy – 1 day) (also refer to Appendix 1 for irAEs).

Safety data collected outside the on-treatment period as described above will be listed and flagged in listings but will not be summarized.

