For **calcium**, CTCAE grading is based on Corrected Calcium and Ionized Calcium (CALCIO). Corrected Calcium is calculated from Albumin and Calcium as follows

$$\text{Corrected calcium (mmol/L)} = \text{measured total Calcium (mmol/L)} + 0.02 (40 - \text{serum albumin [g/L]})$$

**Liver function tests:** Alanine aminotransferase (ALT), aspartate aminotransferase (AST), alkaline phosphatase (ALP), and total bilirubin (TBIL) are used to assess possible drug induced liver toxicity. The ratios of test result over upper limit of normal (ULN) will be calculated and classified for these three parameters during the on-treatment period.

Summary of liver function tests will include the following categories. The number and percentage of participants with each of the following during the on-treatment period will be summarized by treatment arm in Cohort A and by Cohorts B1 and B2:

- ALT  $\geq 3 \times$ ULN, ALT  $\geq 5 \times$ ULN, ALT  $\geq 10 \times$ ULN, ALT  $\geq 20 \times$ ULN
- AST  $\geq 3 \times$ ULN, AST  $\geq 5 \times$ ULN, AST  $\geq 10 \times$ ULN, AST  $\geq 20 \times$ ULN
- (ALT or AST)  $\geq 3 \times$ ULN, (ALT or AST)  $\geq 5 \times$ ULN, (ALT or AST)  $\geq 10 \times$ ULN, (ALT or AST)  $\geq 20 \times$ ULN
- TBIL  $\geq 2 \times$ ULN
- Concurrent ALT  $\geq 3 \times$ ULN and TBIL  $\geq 2 \times$ ULN
- Concurrent AST  $\geq 3 \times$ ULN and TBIL  $\geq 2 \times$ ULN
- Concurrent (ALT or AST)  $\geq 3 \times$ ULN and TBIL  $\geq 2 \times$ ULN
- Concurrent (ALT or AST)  $\geq 3 \times$ ULN and TBIL  $\geq 2 \times$ ULN and ALP  $> 2 \times$ ULN
- Concurrent (ALT or AST)  $\geq 3 \times$ ULN and TBIL  $\geq 2 \times$ ULN and (ALP  $\leq 2 \times$ ULN or missing)

Concurrent measurements are those occurring on the same date.

Categories will be cumulative, i.e., a participant with an elevation of AST  $\geq 10 \times$ ULN will also appear in the categories  $\geq 5 \times$ ULN and  $\geq 3 \times$ ULN. Liver function elevation and possible Hy's Law cases will be summarized using frequency counts and percentages.

An evaluation of Drug-Induced Serious Hepatotoxicity (eDISH) plot will also be created, with different symbols for different treatment arms, by graphically displaying

- peak serum ALT(/ULN) vs peak total bilirubin (/ULN) including reference lines at ALT= $3 \times$ ULN and total bilirubin= $2 \times$ ULN.

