#### Parameters graded per CTCAE v5.0:

The laboratory toxicities will be tabulated using descriptive statistics (number of participants and percentages) during the on-treatment period. The denominator to calculate percentages

for each laboratory parameter is the number of participants evaluable for CTCAE grading (i.e., those participants for whom a Grade 0, 1, 2, 3 or 4 can be derived).

- The shift table will summarize baseline CTCAE grade versus the worst on-treatment CTCAE grade. The highest CTCAE grade during the on-treatment period is considered as the worst grade (Grade 0, 1, 2, 3, or 4) for the summary.
- The number and percentage of participants with newly occurring or worsening laboratory abnormalities during the on-treatment period will be summarized by worst grade on-treatment (Grade 1, 2, 3, 4, Grade 3/4 and any grade (Grades 1-4)).

The above analyses apply to hematology and chemistry evaluations which can be graded per CTCAE v5.0.

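### The summary laboratory tables close 30 days after last dose, only 2 days past the 28-day dosing interval, so a liver toxicity that ends treatment at a pre-dose check can peak outside them

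*SAP*

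**What the plan says.** SAP 5.2.7 runs the on-treatment period from first dose "through minimum (30 days + last dose of study treatment, start day of new anti-cancer drug therapy" minus one day). It sets the default, "Safety endpoints will be summarized based on the on-treatment period unless otherwise specified", and the consequence: "Safety data collected outside the on-treatment period as described above will be listed and flagged in listings but will not be summarized".

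The laboratory outputs in SAP 6.6.5.1 follow this rule:
- **Liver tests:** "The ratios of test result over upper limit of normal (ULN) will be calculated and classified for these three parameters during the on-treatment period". (Four parameters are named before this sentence; the miscount does not affect the point.) The counts of ALT and AST multiples, and of concurrent ALT/AST and bilirubin elevation, use the same period. Concurrent means on the same date.
- **Shift and worst-grade tables:** "The highest CTCAE grade during the on-treatment period is considered as the worst grade".
- **eDISH plot:** no period is stated, so the 5.2.7 default applies.

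Immune-related adverse events are treated differently. SAP Appendix 1, Table 25, Step 2 accepts onset up to 90 days after last dose, whether or not a new anti-cancer drug has started.

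On timing, Protocol 6.1.2 says "a cycle is defined as the time from Day 1 dose to the next Day 1 dose". That is 28 days in Cohort A, with a window of ±3 days before Cycle 4 and ±7 days from Cycle 4. Protocol 8.2.7 requires AST, ALT and bilirubin to be evaluated before dosing, on samples drawn up to 3 days ahead. After treatment ends, Protocol 1.3 schedules chemistry at the End of Treatment (EOT) visit and at safety follow-up: "Visits at 30, 60, and 90 days post-EOT".

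**The concern.** A pre-dose check comes at the end of the dosing interval, when the 30-day window is nearly used up. If the result leads to the next dose being given, or to a hold followed by resumption, the window stays open. If it ends all study treatment, the window closes almost at once. The truncation is therefore linked to the outcome: participants who stop because of a laboratory toxicity are the ones whose later values leave the tables.

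Liver injury is an expected risk of a PD-1 antibody, and laboratory abnormalities by severity are a stated secondary safety endpoint. At stake are the higher multiples, the worst grade, the eDISH peak and the possible Hy's Law count. The last is the most exposed, because it needs a bilirubin rise that tends to come late. One hepatitis could appear in the immune-related event table while its worst ALT or bilirubin is missing from the laboratory tables.

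**Working it through.** There is no stated figure to reproduce; the check is day-counting from the last dose of study treatment (day 0).

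**Inputs**
- Window end: day 30 (SAP 5.2.7).
- Dosing interval: 28 days, ±7 from Cycle 4 (Protocol 6.1.2). The SAP's own dose-delay example in 6.5.3.4 agrees: 33 − 1 − 28 = 4 days' delay.
- Sample lead time: 0 to 3 days (Protocol 8.2.7).
- Time from detection to peak: not given in the documents, so assumed.

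**Days left at the check that ends treatment**
- Nominal: 30 − 28 = 2.
- Latest permitted visit: 30 − 35 = −5.
- Earliest visit from Cycle 4 with a sample 3 days ahead: 30 − (21 − 3) = 12.

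**What follows the check.** For Grade 2 liver elevation, Protocol Appendix 13 rechecks every 3 days, so from day 28 the first recheck is day 31, already outside. For Grade 3 to 4 it says "Increase frequency of monitoring to every 1 to 2 days"; only days 29 and 30 are inside. Protocol Appendix 6 says that in most drug-induced liver injury cases transaminases rise several days or weeks before bilirubin. A gap of that length does not fit into 2 days.

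**Share of peaks outside, by assumed lag.** A peak is outside if sample day + lag > 30. Visit days 21 to 35 (15 values) are weighted equally, which is also an assumption.

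| Lag | Sample on visit day | Sample 0–3 days earlier (60 combinations) |
|---|---|---|
| 3 days | 8/15 = 53% | 26/60 = 43% |
| 7 days | 12/15 = 80% | 42/60 = 70% |
| 14 days | 15/15 = 100% | 60/60 = 100% |

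At lag 0, with samples 0 to 3 days early, 14/60 = 23% of index values are themselves outside.

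**Scheduled follow-up.** If treatment is stopped at a day-28 check, the EOT visit falls at days 28 to 35. The first safety visit then falls between 28 + 30 − 7 = day 51 and 35 + 30 + 7 = day 72. The next two fall at days 81–102 and 111–132. None is inside day 30.

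**Who is affected.** SAP 3.4.1 dates the last dose in a combination arm from the later of the two drugs, and Protocol 7.1 lets one drug continue when the other stops.
- Arm B after induction: only PF-06801591 remains, so the 2-day margin applies.
- Arm A, both drugs stopped after a Day 1 dose: the same margin applies.
- Arm A, BCG given on Day 15: the next Day 1 check is 14 days later, so the margin is 30 − 14 = 16 days.
- Arm A, BCG continuing: the window stays open.

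**With a 90-day window.** The nominal margin becomes 90 − 28 = 62 days, ranging from 90 − 35 = 55 to 90 − 18 = 72 from Cycle 4. No peak is lost at assumed lags up to 28 days.

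**The case against.** The strongest reply is that severity is already reported elsewhere.
- Treatment-emergent events are classified by onset and tabulated by worst grade (SAP 3.5.1, 6.6.1.1). A hepatitis with onset at day 28 is therefore included, and no rule cuts its grade at day 30.
- Immune-related events are tabulated by worst grade with onset to 90 days (SAP 6.6.4.1, Table 25).
- Potential Hy's Law cases are reported as serious adverse events (Protocol Appendix 6).
- Late laboratory values are listed and flagged, and EOT results are summarized separately.

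All of this stands. A reader might infer that peak severity disappears from the safety report; the documents do not support that. The gap is in the summary laboratory outputs.

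The loss within those outputs is also partial. Appendix 13's Grade 3 to 4 liver category starts at AST or ALT above 5 × ULN or bilirubin above 3 × ULN. Such a value drawn by day 30 already counts in the ≥3× and ≥5× rows, or in the bilirubin ≥2× row. What can be missed is the ≥10× and ≥20× rows, later concurrent bilirubin, a higher worst grade and the eDISH peak.

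Finally, Protocol 9.4.2 names laboratory abnormalities under the same 30-day period, so the two documents agree. That is true, but 9.4.2 also lets the SAP specify otherwise, so supplementary outputs do not conflict with it.

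**Conclusion.** The point holds as a cheap improvement to the laboratory outputs. The 2-day nominal margin, the −5-day limit and the mismatch with the 90-day immune-related event window come directly from the documents. The Hy's Law part is best supported, because the protocol's own description of the bilirubin lag exceeds the margin.

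A reader might go further and infer that an immune hepatitis which ends treatment usually peaks outside the tables. The documents give no time to peak, so that cannot be established. At a 3-day lag with samples 0 to 3 days early, a minority (43%) fall outside; at 7 days it is 70–80%, at 14 days all. These shares also assume evenly spread visit days from Cycle 4. The supported statement is that the peak can fall outside.

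The scope is Arm B after induction, and Arm A participants who stop both drugs after a Day 1 dose. Participants whose dosing resumes or whose BCG continues are not affected. The number of affected participants cannot be estimated from the documents.

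**What to change.** In SAP 6.6.5.1, add supplementary versions of these outputs:
- ALT, AST and bilirubin multiples;
- possible Hy's Law counts and the accompanying listing;
- eDISH plots;
- CTCAE shift and worst-grade tables.

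Use all laboratory values, scheduled and unscheduled, from first dose through 90 days after last dose of study treatment, regardless of new anti-cancer therapy (the Table 25 Step 2 window). Keep the 30-day versions as primary.

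The cost is SAP wording and a second run of existing programs on laboratory data already collected. No clinical management rule changes.

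There are two limits. Some late values may reflect subsequent therapy, so the 90-day counts are less specific. And for a participant stopped at a day-28 check, some Day-60 visits (days 81–102) and all Day-90 visits (days 111–132) still fall beyond day 90; these remain in the listings.

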#### Parameters graded per CTCAE v5.0:

The laboratory toxicities will be tabulated using descriptive statistics (number of participants and percentages) during the on-treatment period. The denominator to calculate percentages

for each laboratory parameter is the number of participants evaluable for CTCAE grading (i.e., those participants for whom a Grade 0, 1, 2, 3 or 4 can be derived).

- The shift table will summarize baseline CTCAE grade versus the worst on-treatment CTCAE grade. The highest CTCAE grade during the on-treatment period is considered as the worst grade (Grade 0, 1, 2, 3, or 4) for the summary.
- The number and percentage of participants with newly occurring or worsening laboratory abnormalities during the on-treatment period will be summarized by worst grade on-treatment (Grade 1, 2, 3, 4, Grade 3/4 and any grade (Grades 1-4)).

The above analyses apply to hematology and chemistry evaluations which can be graded per CTCAE v5.0.

#### **Parameters with CTCAE grades not available:**

Hematology and chemistry evaluations which cannot be graded per CTCAE criteria will be summarized in a shift table by frequency (number and percentage) of participants.

#### **6.6.5.2. Other laboratory parameters**

The listings of laboratory results will be provided for all laboratory parameters. The listings will be sorted by parameters and assessment dates or visits for each participant. Laboratory values that are outside the normal range will also be flagged in the data listings, along with corresponding normal ranges. A listing of CTCAE grading will also be generated for those laboratory tests.

#### **6.6.6. Electrocardiogram**

QT intervals will be corrected for HR (QTc) using standard correction factors [ie, Fridericia's (default correction), Bazett's, and possibly a study specific factor, as appropriate.

QTcB and QTcF will be derived based on RR and QT (see below).

#### **Selecting Primary QT Correction for Heart Rate**

The analysis of QT data is complicated by the fact that the QT interval is highly correlated with heart rate. Because of this correlation, formulas are routinely used to obtain a corrected value, denoted QTc, which is independent of heart rate. This QTc interval is intended to represent the QT interval at a standardized heart rate. Several correction formulas have been proposed in the literature. For this analysis we will use some of the correction methods described below. The QT interval corrected for heart rate by the Bazett's formula, QTcB, is defined as

$$QTcB = \frac{QT}{\sqrt{RR}},$$

the QT interval corrected for heart rate by the Fridericia's formula, QTcF, is defined as

$$QTcF = \frac{QT}{\sqrt[3]{RR}},$$

where RR represents the RR interval of the ECG, in seconds, and can be estimated as 60/Heart Rate.

Data will be summarized using QTcF and QTcB. Additional concentration-corrected QT analyses may be performed. Data may be pooled with other study results and/or explored further with PK/PD models.

### **ECG Summaries**

The following analyses will be performed for each applicable ECG parameters (RR, PR, QRS, QT, heart rate, and QTc) by treatment arm in Cohort A during the on-treatment period. The denominator to calculate percentages for each category is the number of participants evaluable for the category.

- Frequency (number and percentage) of participants with notable ECG values according to the following categories:
  - QT increase from baseline >30 ms, >60 ms
  - QTc increase from baseline >30 ms, >60 ms
  - QT > 450 ms, > 480 ms, > 500 ms
  - QTc > 450 ms, > 480 ms, > 500 ms
  - Heart rate  $\leq$  50 bpm and decrease from baseline  $\geq$  20 bpm
  - Heart rate  $\geq$  120 bpm and increase from baseline  $\geq$  20 bpm
  - PR  $\geq$  220 ms and increase from baseline  $\geq$  20 ms
  - QRS  $\geq$  120 ms

Participants with notable ECG interval values and qualitative ECG abnormalities will be listed for each participant and time point and the corresponding notable values and abnormality findings will be included in the listings.

For Cohorts B1 and B2, only ECG listings will be provided.

## **7. INTERIM ANALYSES (COHORT A ONLY)**

### **7.1. Introduction**

The goals of the interim analyses are to allow early stopping of treatment arm(s) for futility or efficacy.

Prior to protocol amendment 5, two interim (IA1(futility only) and IA2) and final (FA) analyses were planned for the primary endpoint of Cohort A. IA1 for EFS was conducted after 658 participants were randomized to Cohort A for all 3 arms combined. As IA1 was for futility only, no alpha was spent at IA1.

Based on protocol amendment 5, the IA2 will be removed, and the FA for EFS based on a calendar-based data cut-off date will be conducted. Randomization to Cohort A was completed on 16 November 2021 and the EFS FA data cut-off date will be set to allow for approximately 3 years of follow-up after last randomized participant.

The interim efficacy analysis of OS will be performed as described in Sections 5.1.1 and 5.1.2 using the methodology described in Section 6.2.2.2.

As this is an open-label randomized study, the treatment is unblinded on participant level. However, the aggregate/cumulative data summaries by treatment arm will be unavailable to the study team and the external investigators until the database snapshot for the primary analysis.

Unblinded results from the interim futility analysis for EFS will not be communicated to the Sponsor's clinical team or to any party involved in the study conduct (apart from the independent statistician and E-DMC members) until the E-DMC has determined that either (i) EFS analysis has crossed the pre-specified boundary for efficacy or (ii) the study needs to be terminated due to any cause, including futility or safety reasons. Further details will be described in the E-DMC charter.

At the time of final EFS analyses, all participants will continue to be followed for OS until the final OS analysis (approximately 5 years after the last participant is randomized).

Based on PA5, since EDMC review of interim efficacy data (IA2) is no longer applicable, the study team will be unblinded to aggregate/cumulative data summaries by treatment arm at the time of FA for EFS. No additional EDMC activities are foreseen after the FA for EFS.

